#### 2.4.7.1.3 *Adverse events of special interest*

**Protocol-defined IAR:** The following summaries will be produced by primary SOC and PT:

- Protocol-defined IARs
- Protocol-defined IARs by the worst severity
- Protocol-defined IARs started during infusion
- Protocol-defined IARs started between 0 hours (exclusive) and 3 hours (exclusive) post end of infusion
- Protocol-defined IARs started between 3 hours (inclusive) and 24 hours (inclusive) post end of infusion
- Protocol-defined IARs started between 24 hours (exclusive) and 72 hours (inclusive) post end of infusion
- Protocol-defined IARs started after 72 hours post end of infusion

Additionally, Hypersensitivity IARs will be summarized by primary SOC and PT.

In case there are IARs identified by the sponsor (before database lock) that the investigator did not agree to be an IAR, sponsor-identified IARs may be added to the list of investigator-identified IARs to define the protocol-defined IARs, and additional summaries may be produced.

**Algorithm-defined IAR:** The summary of algorithm-defined IARs by primary SOC and PT will be provided.

**Pregnancy:** Pregnancies will be provided as part of patient narrative.

**Symptomatic overdose:** The symptomatic overdose data will be provided as part of patient narrative.

**Quantifiable Dose Limiting Toxicities defined based on laboratory values:** As defined in [Section 2.1.3.1](#), the Quantifiable Dose Limiting Toxicities will be provided in a data listing.

#### 2.4.7.1.4 *Adverse events of other interest*

**Infections:** TEAEs of infections are defined under the system organ class of Infections and Infestations.

**Bleeding:** TEAEs of bleeding are defined under the standard MedDRA queries (SMQs) of Hemorrhages (identified using SMQ code 20000038 broad and narrow scope). Bleeding AE data will be summarized by SOC and PT for each age cohort.

#### 2.4.7.1.5 *Serious adverse events*

Summary of Treatment-emergent serious adverse events will be provided by primary SOC and PT.

#### **2.4.7.1.6 Analyses of adverse events by place of infusion**

To assess the comparability between site infusion and home infusion, the following adverse events will be analyzed, pooling patients of different age cohorts. Only adverse events that occurred after the date when the first patient in the study received his/her first home infusion will be included in these analyses.

- Overview of treatment-emergent adverse events
- Treatment-emergent adverse events by SOC and PT
- Treatment-emergent adverse events by severity, and by SOC and PT
- Treatment-emergent adverse events by the latest infusion dose, and by SOC and PT
- Treatment-emergent serious adverse events by SOC and PT
- Protocol defined IARs by SOC and PT
- Protocol defined IARs by severity, and by SOC and PT
- Protocol-defined IARs started during infusion by SOC and PT
- Protocol-defined IARs started between 0 hours (exclusive) and 3 hours (exclusive) post end of infusion
- Protocol-defined IARs started between 3 hours (inclusive) and 24 hours (inclusive) post end of infusion
- Protocol-defined IARs started between 24 hours (exclusive) and 72 hours (inclusive) post end of infusion
- Protocol-defined IARs started after 72 hours post end of infusion
- Algorithm-defined IARs

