8.1.1 Treatments administered

Patients will receive olipudase alfa every 2 weeks (± 3 days). Home infusions may be possible. To be eligible for home infusions, patients must meet the criteria in [Section 10.2.1](#).

Patients will start this study at the same dose they were receiving at the end of their primary study, provided that they have not missed more than 1 biweekly dose between studies.

All patients will have a visit 2 weeks (± 3 days). Quarterly visits will occur at the site. If the site visit is not possible due to site closure or extenuating circumstances that prevent an in-person site visit (eg, during COVID-19 pandemic) and home infusion is already approved for the eligible patient, quarterly visits will be done at home. Quarterly visit specific assessments that need a site visit will not be done at that time and will be done as unscheduled as soon as site visits become available. In such a case, some of the quarterly visit assessments may be done by home nurse (eg, lab sampling) and by the site through the phone (eg, Health-related quality of life instruments). Telehealth visits are an acceptable alternative to site visits, if site visits are not possible during a regional or national emergency declared by a governmental agency such as the COVID-19 pandemic due to site closure or extenuating circumstances that prevent an in-person site visit, in accordance with institutional policy and with applicable country-specific regulations.

Dose reintroduction regimens may be required for patients who have missed more than 1 dose between studies or during this study (LTS13632), depending on their usual dose. For patients receiving home infusions who have missed 2 or fewer doses, the investigator can decide whether reintroduction should occur at the hospital/study site or via home infusion. For patients who have missed 3 or more doses ≥ 0.6 mg/kg, reintroduction of olipudase alfa should occur at the hospital/study site. If the site visit is not possible during a regional or national emergency declared

by a governmental agency such as the COVID-19 pandemic due to site closure or extenuating circumstances that prevent an in-person site visit, reintroduction may be done via home infusion.

Olipudase alfa reintroduction guidance will depend on the patient's usual dose and the number of missed infusions:

- If a patient misses 1 dose, continue at the dose previous to the missed dose.
- If a patient misses 2 doses:

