10.2.1 Home infusions

Home infusion may be possible. Patients must meet the eligibility requirements outlined below. In addition, the investigator and the sponsor must agree that home infusion is appropriate. To receive home infusions, the following criteria must be met:

- The investigator must agree in writing that home infusion is appropriate for the patient.
- The patient, or the pediatric patient's parent(s) or legal guardian(s), must be willing and able to comply with home infusion procedures.
- The patient must, in the investigator's (or designee's) opinion, have been clinically stable with no history of moderate or severe IARs for at least 6 months, and must be on a stable olipudase alfa dose. No infusion rate increases will be allowed while a patient is receiving home infusions.
- The patient must have no ongoing (not yet recovered) SAEs that, in the opinion of the investigator, may affect the patient's ability to tolerate the infusion.
- Home infusion infrastructure, resources, and procedures must be established and available according to applicable regional regulations.
- For patients experiencing an IAR while being infused at home, the investigator should assess whether or not it is safe for the patient to continue to be treated via home infusion or return to the study site for their following infusion and when the patient would be ready to resume home infusion. In case home infusion continues, the investigator will guide the home infusion staff on the measures to be followed for subsequent infusion to manage the IAR (eg, infusion interruption, premedication, change the infusion rate, etc. See Treatment of infusion-associated reactions in Section 8.6.1).
- If recurrent IARs or hypersensitivity reactions occur, the investigator should assess whether or not it is safe for the patient to continue to be treated via home infusion.
- If a severe hypersensitivity reaction or an anaphylaxis reaction occurs, during an infusion given at home, treatment will be discontinued immediately, and appropriate medical treatment will be initiated. The patient will return to the study site for further management

until the investigator agrees with the sponsor that it is safe for the patient to continue to be treated via home infusion. See [Section 8.6](#) for details on severe hypersensitivity and anaphylaxis management.

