#### **2.4.7 Analyses of safety data**

The safety results will be presented using the safety population. Unless specified otherwise, the displays will include the original study data along with data collected in this study. Patients will be summarized and displayed by original study identifier, age cohort and overall. Safety data will be reported up to and including the time of treatment withdrawal, and follow-up for AEs, where applicable. The baseline value is the last available value before the first infusion of olipudase alfa in the original study, except for hematology parameters and possibly ECG parameters. For complete definition of baseline, refer to [Section 2.6.1](#).

For all safety data, the observation period in this study is the **on-treatment period**, which is defined as the time from the first infusion of IMP (included) from original study to the end of the current study

The following definitions regarding potentially clinically significant abnormality (PCSA) will be applied to laboratory parameters, vital signs and ECG:

- The PCSA values are defined as abnormal values considered medically important by the sponsor according to predefined criteria/thresholds based on literature review and defined by the sponsor for clinical laboratory tests, vital signs, and ECG. These values are provided in [Appendix A](#).
- PCSA criteria will determine which patients had at least 1 PCSA taking into account all evaluations performed, including unscheduled or repeated evaluations.
- Before determining a value as PCSA, the value will be rounded to the precision that the PCSA criterion is defined.

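### The home-versus-site adverse event comparison is confounded by home-infusion eligibility and has no place-specific denominator, so it cannot support comparability as planned.

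*SAP*

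**What the plan says.** The stated aim of SAP 2.4.7.1.6 is "To assess the comparability between site infusion and home infusion", done by "pooling patients of different age cohorts". SAP 1.6 lists this as a new analysis in this version. The section names an overview, TEAE tables (including one by severity and one by latest dose), an SAE table and several IAR tables. The sole restriction on the data is "Only adverse events that occurred after the date when the first patient in the study received his/her first home infusion will be included".

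Four other provisions decide who falls on each side:

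- **Entry to home infusion.** Protocol 10.2.1 sets this condition for the patient: "clinically stable with no history of moderate or severe IARs for at least 6 months, and must be on a stable olipudase alfa dose".
- **Leaving home infusion.** After an IAR at home, the investigator decides whether the patient stays on home infusion or should "return to the study site for their following infusion". After a severe hypersensitivity or anaphylactic reaction the patient goes back to site.
- **Reintroduction.** After 3 or more missed doses of at least 0.6 mg/kg, Protocol 8.1.1 says "reintroduction of olipudase alfa should occur at the hospital/study site", with an exception for emergencies. After 2 or fewer missed doses the investigator chooses the place.
- **Original-study data.** SAP 2.4.7 says "Unless specified otherwise, the displays will include the original study data along with data collected in this study". SAP 2.4.7.1.1 defines TEAEs to include those starting in the original study. Section 2.4.7.1.6 does not say otherwise.

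Home patients also return regularly: "Quarterly visits will occur at the site" (Protocol 8.1.1). SAP 2.4.7.1.1 plans event counts and numbers and percentages of patients, with the safety population as denominator and patient-years on selected tables. No rule assigns an event, or exposure, to a place.

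**The concern.** The main outcome compared, the IAR, is also an entry criterion for one of the two groups and a reason for leaving it. A calendar date common to all patients removes neither selection. It does not use eligibility, dose phase or the patient's own first home infusion.

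If the site tables show more IARs, a reader given a comparability aim may conclude that home infusion is at least as safe, when the difference reflects who is allowed home and in which treatment phase. A real but moderate excess at home could be hidden. Without a denominator tied to place, a reader could also draw the opposite conclusion from the number of infusions alone.

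**Working it through.** The documents give no event rate, margin or sample size for this comparison, so there is no planned figure to reproduce. All rates below are assumptions.

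**1. General size of the bias, per infusion.** Let e be the share of site infusions that are ineligible, escalating or reintroducing, and k their event rate relative to stable, eligible infusions. With no true effect of place:

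site rate / home rate = 1 + e(k − 1)

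- e = 10%, k = 1.5: 1 + 0.10 × 0.5 = 1.05
- e = 20%, k = 3: 1 + 0.20 × 2 = 1.40
- e = 50%, k = 5: 1 + 0.50 × 4 = 3.00

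The same number is the break-even point: a true home excess below it is hidden, and one above it still shows.

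**2. One component, original-study escalation, if it overlaps the date.**

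- Protocol 17.2.6 dates the home option to 23 March 2016. Protocol 17.2.4 dates the amendment raising DFI13803 from 12 to about 20 patients to 21-Aug-2017. Assume that the 20 − 12 = 8 later children fall after the cutoff.
- DFI13803 lasted 64 weeks (SAP 2.4), so 8 × 64/2 = 256 original-study site infusions.
- Assume escalation takes at most 26 weeks, the whole adult treatment period (Protocol 4.1): 8 × 13 = 104 infusions. The other 256 − 104 = 152 are taken as stable.
- Assume an IAR probability p of 3% to 10% in escalation, 1% on every stable infusion at either place, and N = 250 to 1000 further stable site infusions.

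Site rate = [104p + (152 + N) × 0.01] / (256 + N)

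- p = 3%, N = 1000: (3.12 + 11.52)/1256 = 1.17%
- p = 5%, N = 500: (5.20 + 6.52)/756 = 1.55%
- p = 10%, N = 250: (10.40 + 4.02)/506 = 2.85%

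Against 1% at home, the ratio runs from 1.17 to 2.85 with no true difference. Ineligible patients, reintroductions and patients returned after a home IAR are not in this figure.

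**3. Counts and percentages.** Take 25 patients with 26 infusions a year, home patients having 4 of theirs at site and 22 at home, and the same 0.1 events per infusion everywhere.

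- 5 patients on home infusion: 5 × 22 = 110 home infusions, 11 events. Site: 5 × 4 + 20 × 26 = 540 infusions, 54 events.
- 20 patients on home infusion: 20 × 22 = 440 home infusions, 44 events. Site: 20 × 4 + 5 × 26 = 210 infusions, 21 events. If 20% of site infusions carry k = 3, this becomes 21 × 1.4 = 29, still below 44.

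Percentages of patients behave the same way. At an assumed 2% per infusion, a home patient has at least one IAR in a year with probability 1 − 0.98^22 = 0.36 at home and 1 − 0.98^4 = 0.08 at site. The planned displays can thus favour either place when the true rates are equal.

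**The case against.** The strongest defence is that this is one descriptive set in a nonrandomized, single-arm study, with no formal safety testing (Protocol 11.6.3), no margin and no decision rule. Place of infusion was never going to be random, and a stated limitation could cover that. It does not cover a section whose stated purpose is comparability.

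The plan also handles some of the problem. One TEAE table is split by latest dose, which partly separates low-dose escalation. The TEAE overview in SAP 2.4.7.1.2 has a row leaving out the original study, and SAP 2.4.7.1.1 promises listings of events starting in the extension. These points stand, but the listings are not by place, and the IAR, severity and SAE tables in 2.4.7.1.6 remain unrestricted. Nothing addresses IAR history.

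The groups also overlap: home patients have quarterly site infusions, some reintroductions may take place at home, and a patient with a home IAR may continue there. This dilutes the bias but does not remove it.

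A reader might go further and infer that home infusion will look safer whatever the truth. The documents do not support that. The bias is finite, and counts can run the other way. Nor do they show that any patient was refused home infusion. The date of the first home infusion is not given, only the date on which the option entered the protocol; the 2017 date is that of an amendment, not of any enrolment. SAP 1.3 and 2.4 still describe 12 pediatric patients, while SAP 1.1 says about 20. Overlap with escalation is therefore plausible, not established.

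**Conclusion.** The point holds. Eligibility, return to site after an IAR and the place of reintroduction are enough to confound the comparison, even if no original-study infusion falls after the cutoff. On a rate basis the bias favours home infusion. Its size is unknown: the 1.2 to 2.9 range rests on assumed IAR rates, 8 overlapping children, escalation of at most 26 weeks and 250 to 1000 other site infusions. Applying escalation-level risk to all 256 original-study infusions would give 1.41 to 5.55, but escalation is only the early part of treatment, so that range should not be used. On the planned counts and percentages, the direction is not determined at all, because no place-specific denominator is defined.

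**What to change.** Add a primary place-of-infusion comparison to SAP 2.4.7.1.6:

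- Restrict it to patients who ever received a home infusion, from each patient's own first home infusion and while on their usual dose. Exclude original-study and reintroduction infusions.
- Attribute each AE and IAR to the place of the latest preceding infusion, and report it per infusion given at that place, with the number of patients contributing at each place.
- Flag site infusions given because of a preceding home IAR, and show results with and without them. Without this step, the within-patient comparison keeps part of the same selection.
- Keep the pooled tables as a description of all infusions, and drop the comparability wording from them.

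The cost is SAP wording and a programming filter on data already collected. The comparison will be smaller, with about 4 site infusions per patient-year. Site visits also carry more assessments, so events may be picked up more readily there. The result would be less biased, not unconfounded, and should be described that way.

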#### **2.4.7.2 Clinical laboratory evaluations**

For parameters that are reported as BQL (below the quantification limit), the results often convey a clinically meaningful change. Therefore, a numerical value is necessary to be imputed for including these in descriptive statistics calculations as well as plotting them in by-patient graphs. For all these parameters the lower limit of quantification (LLOQ) is available in the database. The imputed value for BQL will observe the same precision as reported values, but will be lower than the LLOQ by the minimum of that precision. For example, if a parameter is reported to two decimal places, and its LLOQ is X, then the imputed value of BLQ is (X-0.01). On the other hand, if a parameter is reported to one decimal place, and its LLOQ is X, then the imputed value of BLQ is (X-0.1). Listing will provide data as BQL and <LLOQ where LLOQ will be populated.

Observed values, change from baseline and percent change from baseline to scheduled study time points will be summarized in separate groups of hematology (excluding hemoglobin and platelets which are considered efficacy parameter, hence the analyses have been described in [Section 2.4.8.7](#)), liver function tests, lipids, coagulation, etc. as described in [Section 2.1.3.3](#). By patient plots of WBC, ALT, AST, total bilirubin will be provided. Summary plots over time will also be provided as needed.

Laboratory values will be classified as normal, above normal, or below normal based on normal ranges when provided by the laboratory. Shifts from baseline to scheduled time points, any time during the on-treatment period and the last available value, in the abnormality of any parameters will be provided.

PCSA values for hematology and liver function tests (provided in [Appendix A](#)) during the study (from first infusion in the original study to last available observation) will be summarized. PCSA values for hematology, liver function test and clinical chemistry parameters will be provided in separate listings.

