STATISTICAL CONSIDERATIONS	
Sample size determination
 
Sample size is determined by the number of patients who complete the treatment phase of a previous clinical study of olipudase alfa, sign the informed consent form of the LTS13632 study, and meet the eligibility criteria. It is expected that the sample size for this study will be approximately 25.
 
Analysis populations
 
The safety set will include all enrolled patients who received at least 1 dose (partial or total) of olipudase alfa in the current study.
 
Analysis of safety
 
Safety analyses will include a summary of treatment duration, the total number of infusions received, and the total amount of olipudase alfa received. Frequencies (number and percentage) of patients with 1 or more treatment-emergent AEs will be summarized by the Medical Dictionary for Regulatory Activities System Organ Class (SOC) and preferred term (PT). All treatment-emergent AEs, all treatment-emergent AEs potentially related to olipudase alfa, all treatment-emergent AEs leading to treatment discontinuation and study discontinuation, all treatment-emergent AEs that are infusion-associated reactions, all treatment-emergent serious adverse events (SAEs) (including treatment-related SAEs), and all AEs with fatal outcomes (including fatal treatment-emergent AEs) will be summarized. Other safety variables, including laboratory parameters and vital sign measurements, will be summarized by study visit and by dose.
 
The PK analysis will include all patients who receive at least 1 infusion of study drug after PK analysis informed consent and have evaluable PK data.
 
Other analysis populations, such as for pharmacogenomics, if any, will be defined in the SAP.

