11.6.3.2 Laboratory data and vital sign measurements

11.6.3.2.1 Physical examinations, vital sign measurements, electrocardiograms, and echocardiograms

Observed values and changes from baseline (as applicable) will be summarized descriptively overall and by highest tolerated dose and/or by dose received prior to evaluation. Outlier summaries for the ECG parameters (eg, QTc) will be created for the safety set.

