11.6.3.2.2 Clinical laboratory tests

Observed values and changes from baseline to study time points will be summarized descriptively overall and by highest tolerated dose and/or by dose received prior to evaluation. All laboratory values will be classified as normal, above normal, or below normal based on normal ranges provided by the laboratory. Frequencies of CS abnormal values and shifts from baseline to study time points will be summarized. Patient listings of biomarkers will be provided.

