11.6.3.3 Immune response assessments

Immune response assessments will be analyzed in the safety set. The presence, absence, and titers of serum anti-olipudase alfa IgG antibodies will be summarized. The data will be summarized over time overall and by the dose level of the infusion prior to or during the evaluation.

Levels of acute phase reactants, serum tryptase, complement activation, neutralizing antibodies, and anti-olipudase alfa antibodies (IgG and IgE) obtained in response to an IAR, and skin testing results (if available), will be presented in patient listings, if applicable.

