## 1.5 MODIFICATIONS TO THE STATISTICAL SECTION OF THE PROTOCOL

In the section of statistical consideration of the Amended Clinical Trial Protocol 4 Section 11.6.3, treatment period is defined as time from first dose to the last dose of IMP +14 days. In this SAP, in order to incorporate the data from original study (ie, adult study DFI13412 or pediatric study DFI13803), the treatment period definition is changed to “the time from the first infusion of IMP (included) from original study to the end of the current study”.

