#### **2.4.7.1.2 Treatment-emergent adverse events**

An overview of TEAEs will be provided to include (potentially related is defined as either “related” or “possibly related” as assessed by the investigator):

- TEAEs
- TEAEs excluding original study
- TEAEs potentially related to study treatment

- TEAEs by the worst severity
- TEAEs leading to treatment discontinuation
- TEAEs leading to study withdrawal
- TEAEs leading to dose reduction
- TEAEs leading to study treatment interruption
- Protocol-defined IARs
- Algorithm-defined IARs
- Treatment-emergent serious adverse events
- Treatment-emergent serious adverse events potentially related to study treatment
- TEAEs with fatal outcome (Deaths)
- Treatment-emergent pregnancies
- TEAEs which are considered symptomatic overdose
- Dose-limiting toxicities (collected in the adverse event log page in e-CRF, see protocol Section 8.1.6 for details)

The following summaries will be produced by primary SOC and PT:

- TEAEs
- TEAEs by the worst severity (ie, mild, moderate, or severe)
- TEAEs potentially related to study treatment
- TEAEs potentially related to study treatment, by the worst severity (ie, mild, moderate, or severe)

The most common TEAEs will be summarized by SOC and PT for patients from pediatric study DFI13803 and for patients from adult study DFI13412 in separate tables. The criteria of most common TEAEs are the following, which will be applied to the two populations separately:

- the number of events of a preferred term is more than or equal to 2% of the number of all TEAEs in the population, AND
- the number of patients who had this event is more than or equal to 2.

For the above summary for patients from pediatric study, it will be summarized by age cohort and overall.

TEAEs by the latest infusion dose immediately preceding the start of AE will be provided by SOC and PT.

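### SAP 2.4.7.2 drops the laboratory summary by dose that the protocol plans, and SAP 1.5 does not declare it; three other groups of assessments lose their by-dose summaries in the same way

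*SAP*

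**What the plan says.** **Protocol, laboratory data.** For the values as well as their changes, Section 11.6.3.2.2 states: "changes from baseline to study time points will be summarized descriptively overall and by highest tolerated dose and/or by dose received prior to evaluation". The synopsis (Statistical Considerations, analysis of safety) agrees: "Other safety variables, including laboratory parameters and vital sign measurements, will be summarized by study visit and by dose".

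**SAP, laboratory data.** Section 2.4.7.2 states: "Observed values, change from baseline and percent change from baseline to scheduled study time points will be summarized in separate groups". It adds by-patient plots, shift tables and summaries of potentially clinically significant abnormalities (PCSA). None of these is by dose.

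**SAP, general safety rule.** Section 2.4.7 states: "Patients will be summarized and displayed by original study identifier, age cohort and overall". Section 2.4 sets the same groupings for the SAP as a whole.

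**SAP, declared departures.** Section 1.5 contains one item, introduced by the words "the treatment period definition is changed to"; under it, the period begins with the first infusion in the original study and lasts until this study ends. Section 1.6, which lists what changed since the previous SAP version, says nothing about dose groupings.

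**The concern.** SAP 1.5 is where a reader looks for differences between the SAP and the protocol's statistical section. It cites protocol Section 11.6.3, the parent of the laboratory section, yet the loss of the by-dose summary is not there. A reader of the study report could not tell whether the table was dropped on purpose or overlooked.

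The subject is the primary objective, safety. The rationale for Amendment 06 (Protocol 17.2.1) names transient transaminase elevation during dose escalation as an important identified risk. A summary of liver tests by dose is the planned aggregate output that bears most directly on it. Under the SAP as written, that output would not be produced.

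**Working it through.** No arithmetic is at stake in the finding itself. The check sets the two documents side by side.

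**1. Is the by-dose summary optional in the protocol?** No. The and/or in 11.6.3.2.2 offers a choice between two dose groupings: the highest dose the patient tolerated, or the dose given before the assessment. It does not offer a choice between dose and no dose. The synopsis has no such alternative.

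**2. Could a version difference explain the gap?** The SAP is based on Amendment 04; the protocol supplied is Amendment 07. The change tables for Amendments 05, 06 and 07 list no edit to 11.6.3.2. The only Section 11 entry in them is a renumbering of 11.1.1. The by-dose text was therefore very probably in Amendment 04, but that version is not supplied, so this is an inference.

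**3. Where is dose planned, and where is it kept?**

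| Data | Protocol | SAP |
|---|---|---|
| Laboratory tests | 11.6.3.2.2 and synopsis: overall and by dose | 2.4.7.2: by time point and panel; no dose |
| Physical examination, vital signs, ECG, echocardiogram | 11.6.3.2.1: "will be summarized descriptively overall and by highest tolerated dose and/or by dose received prior to evaluation" | 2.4.7.3 to 2.4.7.6: no dose |
| IgG antibodies | 11.6.3.3: "The data will be summarized over time overall and by the dose level of the infusion prior to or during the evaluation" | 2.4.7.11: no dose |
| Metabolites | 11.6.4: by dose level and time point | 2.4.9.1: by visit; no dose |
| Adverse events | 11.6.3.1: by dose level of the preceding or current infusion | 2.4.7.1.2: "TEAEs by the latest infusion dose immediately preceding the start of AE will be provided by SOC and PT" |
| Pharmacokinetic parameters | 11.6.4: by dose level and study week | 2.4.9.2: dose level kept |

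The first four rows lose dose and the last two keep it. The SAP therefore still treats dose as relevant to safety, through the adverse-event table.

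**4. Does any general rule bring dose back?** No. SAP 2.4 and 2.4.7 group by original study, age cohort and overall only.

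**5. Is the omission declared?** No. SAP 1.5 has its single item on the treatment period, and SAP 1.6 is silent.

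**6. Does dose vary in the data to be summarized?** Yes. SAP 2.4.7 includes original-study data in the safety displays unless stated otherwise. In the adult study the dose rose from 0.1 to 3.0 mg/kg (Protocol 4.1), a range of 3.0 / 0.1 = 30-fold. Within the extension, reduced doses after missed infusions (Protocol 8.1.1) and individual adjustments (8.1.4) add some variation. Visit is a weak stand-in for dose: SAP 2.4 follows this study's measurement schedule in its displays, and liver tests on that schedule are every 3 months (SAP 2.1.3.3).

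**The case against.** **The escalation results are reported elsewhere, and extension dosing is stable.** SAP 2.4 says original-study results are included to show continuity and refers the reader to the original study report for detail. Patients enter the extension at the dose on which they finished (Protocol 8.1.1). All five adults stayed at 3.0 mg/kg once they reached it (Protocol 4.1), so a table by highest tolerated dose would be a single column for them. Most of this stands. It makes the loss small and favors the other grouping, dose received before the assessment. It does not remove the protocol's commitment, nor the need to declare a departure from it.

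**Liver-test rises are not lost.** This also stands. PCSA counts use all evaluations, including unscheduled and repeated ones (SAP 2.4.7). Shift tables cover any time on treatment, and ALT, AST and total bilirubin are plotted by patient (SAP 2.4.7.2). Dose-limiting toxicities based on laboratory values are listed (SAP 2.4.7.1.3). Rises recorded as adverse events enter the adverse-event tables, including the one by dose. A reader might infer that the SAP would hide transaminase elevations; the documents do not support that.

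**Reintroduction after missed doses.** A reader might go further and infer that the SAP also errs by having no laboratory output per reintroduction episode, measured from the re-escalation baseline in Protocol 8.1.5. The documents do not support this either. No section plans an analysis by episode, and Protocol 11.4 sets one analysis baseline throughout, from the previous study. The re-escalation baseline serves a clinical instruction on repeating tests and adjusting dose. It entered with Amendment 06, after the version on which the SAP is based. The absence of an episode table is therefore not a departure from the protocol.

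**Conclusion.** The finding holds as an undeclared departure of the SAP from the protocol. Laboratory summaries by dose are planned in two places in the protocol and appear nowhere in the SAP. Three further groups of assessments lose their by-dose summaries in the same way, and none of these losses is declared.

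Severity is minor. The outputs are descriptive, the study has about 25 patients, dosing in the extension is mostly constant, and individual rises remain visible through several other outputs. What is lost is an aggregate view of liver tests by dose, on the primary objective and for a risk the sponsor itself names.

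The conclusion rests on one assumption: that the by-dose text already stood in Amendment 04. The later change tables point to this but do not prove it. If the text was added later, the SAP as supplied is out of step with the current protocol, and the remedy is the same. The documents do not show how many laboratory values were taken at each dose level, so how informative the restored table would be cannot be stated in advance.

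**What to change.** Add to SAP 2.4.7.2 a descriptive summary of observed values and changes from baseline by dose received before the assessment, at least for liver function tests. Include the original-study escalation data that the safety displays already use, and keep the single baseline from the original study. State in SAP 1.5 which of the other by-dose summaries stay dropped (remaining laboratory panels; physical examination, vital signs, ECG and echocardiogram; IgG antibodies; metabolites), with a short reason.

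The cost is one descriptive table and one sentence. It needs no new data and no inferential analysis.
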